8.3. END OF STUDY

The end of the trial corresponds to the last follow-up of the last patient.

9. Statistical considerations

9.1 Sample size

The main objective is the comparison of overall survival in the regorafenib and REGIRI combination (Regorafenib + Irinotecan) arms in mCRC patients harboring Cyclin D1 A/A genotype.

The aim is to increase the median overall survival from an estimated baseline of 7 to 15 months corresponding to 1-year OS of 30% to 57%, respectively with a HR=0.47. A total of **55 events are required** to detect this difference if it is true with 80% power and using a 2-sided log-rank test at the 5% level of significance.

A total number of required patients is 68 without drop-out.

Considering 15% additional patients lost to follow-up on estimated patients number, the sample size is 78 patients (2*39) to observe the required number of events.

Because the A/A CCND1 genotype is present in 25% of patients with metastatic colorectal cancer, 312 patients will need to be screened.

No interim analysis was planned.

9.2 Study populations

Different population of patients may be defined for the analysis:

- Per-Protocol (PP) population = all patients in the ITT population without major protocol deviations that impact assessment of efficacy.
 - The PP Analysis will be used to perform sensitivity analysis for the primary endpoint.
- Intent To Treat (ITT) population = all randomized patients analyzed in their randomized arm.
- Eligible population: all patients without major inclusion criteria (Cl n°1, n°3, n°4, n°5, n°8) or non-inclusion violation (n°2, n°3, n°7, n°8).
- Safety population = all treated patients who received at least one dose of treatment
- Modified Intent To Treat (ITT) population = eligible population in their randomized arm.

9.3 Statistical methods

A Statistical Analysis Plan (SAP) will be written before the database is locked. Populations are defined in section 9.2.

All statistical analyses will be performed on ITT population.

Safety analysis will be performed on safety population

Sensitivity analysis will be performed on Modified Intent To Treat (ITT) population for primary endpoint.

Descriptive analyses (in each arm) will be performed using median and range for continuous parameters, frequency and percentage for categorical variables.

Baseline characteristics of randomized patients in each arm will be compared by Kruskal-Wallis tests or Wilcoxon for continuous variables, or chi 2 or Fisher exact test for categorical variables

The primary efficacy endpoint of OS will be compared using a two-sided stratified log-rank test. The analysis will be stratified by RAS. Kaplan-Meier (KM) estimates for OS and KM survival curves will also be presented for each group. The KM estimates at time points such as 6 months and 12 months, together with corresponding 95% confidence intervals as well as the differences of these estimates will be calculated between the REGIRI and Regorafenib arms.

With regard to the secondary efficacy endpoint PFS, the 2 treatment groups will be compared using a log-rank test stratified by RAS. Hazard ratios and 95% CI will be provided. KM estimates and KM curves will also be presented for each treatment arm. The KM estimates at time points such as 3 months and 6 months, together with corresponding 95%

Protocole NEXT-REGIRI -Version 6.0 du 09/11/2023

confidence intervals as well as the differences of these estimates between the REGIRI arm and the Regorafenib arm will also be calculated.

Objective response rate as well as DCR will be compared between treatment groups using the Cochran-Mantel-Haenszel test. Estimates and 95% confidence intervals will be computed for each treatment arm. The differences in ORR and DCR between the REGIRI and regorafenib arms and the corresponding 95% confidence intervals will also be calculated.

Summary statistics will be displayed for all best response categories: CR, PR and SD.

Descriptive summary tables will be presented for all safety parameters by each treatment group. All AEs, as well as drug-related AEs and SAEs will be summarized by NCI-CTCAE version 5 (appendix 9) categories and worst grade.

PRO data as measured by the EORTC QLQ-C30 (appendix 2) will be analyzed to assess differences in health-related quality of life (HRQOL) values between treatment arms.

HRQOL scores were described for each assessment and compared either between treatment arms (rank sum test). The missing data pattern was studied by the comparison of the baseline characteristics between patients who either completed baseline HRQOL questionnaires or not. The compliance of the patients was also described using fill rate at each visit and for each questionnaire.

Longitudinal analyses were performed using two approaches:

- (1) A LMM analysed the evolution of scores through time and combined fixed effects [Cnaan A, Laird NM, Slasor P. Using the general linear mixed model to analyse unbalanced repeated measures and longitudinal data. Stat Med 1997;16:2349-80.+ Fairclough DL. Design and analysis of quality of life studies in clinical trials. 2002.] for study group, time factors, treatment-by-time interaction effects and random effects allowing specific correlations between observations for a particular patient. This mode I assumed no difference between the treatment arms at baseline.
- (2) A time to event approach considered the definitive deterioration of a HRQOL score as an event. Osoba et al. [Osoba D, Rodrigues G, Myles J, Zee B, Pater J.

Interpreting the significance of changes in health-related quality-of-life scores. J Clin Oncol 1998;16:139-44.] showed that a mean change of 5-10 pts, 10-20 pts and >20 pts in a QLQC30 score corresponds to a "small", "moderate" and "large" change in HRQOL. This definition was applied to indicate the clinical relevance of any differences. TUDD was defined as the time from randomisation to the first score deterioration with a 10-point minimal

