2.2 Endpoints

2.2.1 Primary endpoint

Median Overall survival presented with its confidence interval at 95%, estimated from the randomization date to the date of death, whatever the cause, using the Kaplan-Meier method.

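### Does the primary survival analysis go wrong because section 9.3 names no treatment hazard ratio for OS?

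*Combined protocol and SAP*

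**What the plan says.** All the relevant text is in the protocol; the separate analysis plan is still to come ("A Statistical Analysis Plan (SAP) will be written before the database is locked", section 9.3).

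- **Design effect (section 9.1).** Median OS is to rise from 7 to 15 months, "corresponding to 1-year OS of 30% to 57%, respectively with a HR=0.47", with 55 events, 80% power and a two-sided 5% log-rank test. The total goes from 68 to 78: "Considering 15% additional patients lost to follow-up on estimated patients number".
- **OS endpoint (section 2.2.1).** "Median Overall survival presented with its confidence interval at 95"%, by Kaplan-Meier. This is a summary within each arm.
- **OS analysis (section 9.3).** "The primary efficacy endpoint of OS will be compared using a two-sided stratified log-rank test. The analysis will be stratified by RAS". Then come survival curves and "The KM estimates at time points such as 6 months and 12 months, together with corresponding 95% confidence intervals", with the between-arm differences of those estimates named later in the same sentence.
- **PFS analysis (section 9.3).** A log-rank test stratified by RAS, followed by "Hazard ratios and 95% CI will be provided".
- **Response and disease control (section 9.3).** "The differences in ORR and DCR between the REGIRI and regorafenib arms and the corresponding 95% confidence intervals will also be calculated".

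The only hazard ratios in section 9.3 that involve OS are prognostic ones, per 10 points of baseline QLQ-C30 score. They do not compare the arms.

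**The concern.** The trial is sized on a hazard ratio, its primary test is the one that goes with a hazard ratio, and the plan commits to a hazard ratio for a secondary endpoint but not for the primary one. Read strictly, the OS confidence intervals attach to the Kaplan-Meier estimates in each arm and not clearly to their difference, whereas the response-rate sentence gives the difference a CI outright.

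If nothing were added, a reader would see a p-value, two medians with CIs, and survival differences at two times. Those differences use less information than the log-rank test and can point the other way. The time points are also offered as examples, so in an open-label trial one could be stressed after the data are seen. At stake is how the size of effect is presented. The test decision is not affected.

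**Working it through.** **1. Reproduce the plan's figures.** Inputs from section 9.1: medians 7 and 15 months, hazard ratio 0.47, two-sided 5%, 80% power, 1:1.

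- Hazard ratio from the medians: 7/15 = 0.467. From the 1-year rates: ln 0.57 / ln 0.30 = 0.467.
- Exponential 1-year OS: 0.5^(12/7) = 0.305 and 0.5^(12/15) = 0.574, against the stated 30% and 57%.
- Schoenfeld events: 4 × (1.960 + 0.842)² / (ln HR)². At 0.47 this is 31.40/0.570 = 55.1; at 7/15 it is 31.40/0.581 = 54.1, rounded up to 55. Power with 55 events is 79.9% and 80.7% respectively.
- Total: 68 × 1.15 = 78.2, stated as 78.

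The test and its event count are sound.

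**2. What each endpoint is promised in section 9.3.**

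| Endpoint | Between-arm estimate | 95% CI on it |
|---|---|---|
| OS | differences in KM estimates at times such as 6 and 12 months | can be read either way |
| PFS | hazard ratio; KM differences | yes for the hazard ratio |
| ORR, DCR | difference in rates | yes |

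The PFS sentence on KM differences has the same loose wording as the OS one. That points to drafting rather than a choice to treat OS differently.

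**3. What the missing estimate would look like.** With 55 events at 1:1, SE(ln HR) ≈ 2/√55 = 0.270.

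- An observed 0.47 gives 0.47 × exp(±1.96 × 0.270) = 0.28 to 0.80.
- The largest hazard ratio significant at 5% is exp(−1.96 × 0.270) = 0.59.
- For comparison, the design difference at 12 months is 0.57 − 0.30 = 0.27. With 39 per arm and no censoring, its SE is √(0.30×0.70/39 + 0.57×0.43/39) = 0.108, so the 95% CI is 0.06 to 0.48.

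At the design values both intervals exclude no effect.

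**4. How often the planned summaries disagree with the test.** Simulation, 4,000 trials per scenario: 78 patients, exponential survival, uniform accrual over 64 months, blocks of 4 within RAS, half RAS-mutant, analysis at the 55th death. Loss of 15% is placed uniformly in months 0 to 6; that timing is an assumption.

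| | 15% lost | no loss | true HR 0.60, 15% lost |
|---|---|---|---|
| *Among significant trials* | | | |
| 12-month difference CI includes 0 | 25% | 24% | 36% |
| 6-month difference CI includes 0 | 42% | 45% | 52% |
| both include 0 | 16% | 16% | 23% |
| stratified HR CI includes 1 | 1% | 1% | 2% |
| *Among non-significant trials* | | | |
| at least one difference CI excludes 0 | 24% | 23% | 17% |
| stratified HR CI excludes 1 | 0% | 0% | 0% |

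The log-rank test was significant in 77% of trials in the first scenario. Repeat runs with separate code moved the figures they covered by no more than about 3 points. A RAS-mutant share of 30% or 70% moved none by more than 4.

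**5. What the simulation shows.** The disagreement arises only if the differences do carry CIs, which is the reading under which OS already has a between-arm estimate with an interval. A survival difference at one time and a log-rank test measure different things, so at 78 patients some disagreement is expected. The near-perfect agreement of the hazard ratio is almost built in: the log-rank test is the score test of the stratified Cox model, and the usual CI is its Wald counterpart.

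**The case for a change.** The strongest case for a change is that it would be cheap. The analysis plan is unwritten, one sentence would close the gap, and a team that wrote a hazard ratio into the PFS paragraph and left it out for the primary endpoint has not committed to it. A positive trial would have about a one-in-four chance of printing a 12-month difference whose CI includes 0 beside a significant p-value, and readers will want to set the result against 0.47.

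The textual point stands: no OS treatment hazard ratio is named, and the PFS sentence does not stretch to cover OS. Three things limit its weight.

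- Section 9.1 gives the design effect in three linked forms: medians, 1-year rates and hazard ratio. The plan estimates the first two directly, so a reader can already compare the result with the design.
- Little is left open. Section 9.3 puts all efficacy analyses on the ITT population and fixes RAS as the stratum for OS; the stratified Cox estimate follows from those choices.
- Late choice of a time point is a weak worry. Section 9.3 names 6 and 12 months, section 9.1 already uses 1 year, and no conclusion depends on either.

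**Conclusion.** No change to the plan follows. Section 9.3 leaves out a reporting detail that the analysts can be expected to supply in the analysis plan, as they already have for PFS. Following the text as it stands gives a valid primary test and the same decision on OS; the effect on type I error, power and sample size is nil. What is unstated is an estimate whose 95% CI would run from about 0.28 to 0.80 at an observed hazard ratio of 0.47 and 55 events.

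The simulated percentages rest on exponential survival, the assumed timing of loss, and analysis at the 55th death. The protocol requires 55 events but does not say that the 55th death triggers the analysis; sections 3.1 and 9.1 give calendar dates and an event count side by side. With no loss, the 55th death fell before month 64 in 91% of simulated trials, with about 73 patients enrolled on average. A fixed cut at month 69 changed the percentages little. The verdict does not depend on these figures, because the plan bases no decision on the summaries they describe.

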10.1 Adverse Events

10.1.1 Definition

An Adverse Event (AE) is defined as "Any untoward medical occurrence in a patient or clinical investigation subject administered an investigational product and which does not

Protocole NEXT-REGIRI -Version 6.0 du 09/11/2023

Page **68** sur **86**

necessarily have a causal relationship with this treatment". An AE can therefore be any unfavorable and unintended sign (for example: an abnormal laboratory finding), symptom, disease, or worsening of a pre-existing medical condition temporally associated with the use of an investigational product, whether or not considered related to the investigational product.

Only abnormal laboratory findings which are clinically significant should be considered an AE. Abnormal laboratory findings are clinically significant if an active medical intervention is indicated, such as a dose modification of the investigational product; an interruption of the investigational product; the withdrawal of the investigational product; the introduction of a (symptomatic) treatment; the performance of additional diagnostic procedures; the increase in monitoring frequency.

An AE related to the investigational product is also called an adverse reaction.

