- Chemistry panel: albumin, lipase, phosphate, glucose, serum creatinine, clearance calculated according CKD-EPI (appendix 7)
- Hepatic panel: Aspartate Amino-Transferase (AST), Alanine Amino-Transferase (ALT), bilirubin (total and direct), GGT, alkaline phosphatase, Lactic Dehydrogenase (LDH)
- Urine analysis by urinary dipstick. If results of protein ≥ 3+, then quantification of proteinuria on a 24-hour urine collection must be done.
- Drug accountability (pharmacy)
 Verify patient's diary. It will allow to patient to write down his oral intakes and blood pressure values

The following assessments should be performed on day 15 of cycle 1 and 2:

Stivarga® (Regorafenib - arm B):

• these laboratory evaluations are required: Aspartate Amino-Transferase (AST), Alanine Amino-Transferase (ALT), bilirubin (total and direct)

The following assessments should be performed on day 22 of cycle 1 and 2:

REGIRI (arm A):

- Phone call by a treatment nurse for knowing if there are any adverse events and blood pressure value (current state of the art)
- These laboratory evaluations are required: Aspartate Amino-Transferase (AST),
 Alanine Amino-Transferase (ALT), bilirubin (total and direct)

The following assessments should be performed at each evaluation i.e (every 8 weeks):

REGIRI or Regorafenib:

 Tumor markers CEA (Carcino-Embryogenic Antigen), CA 19.9 (Carbohydrate Antigen 19-9)

 Radiological tumor assessment using the RECIST criteria, version 1.1 (see Appendix 5) must be performed. (CT scan of the abdomen, pelvis and chest or hepatic MRI and CT scan of the pelvis and chest without injection)

A PET scan is not acceptable for radiological evaluation. Throughout the study, the identical lesions to those identified and measured at baseline must be evaluated using the same technique, and preferably by the same radiologist. Copies of all CT scans performed for tumor assessment in non-progressive enrolled patients will be stored on CDs at the site

 EORTC QLQ-C30 (appendix 2) questionnaires will be completed by the patient at each evaluation i.e 8 weeks

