ANC < 1500/mm ³	J21*	No dose modification + G-CSF

Protocole NEXT-REGIRI -Version 6.0 du 09/11/2023

Page **44** sur **86**

and Platelets > 100 000/mm ³		
Platelets < 100 000/mm ³	121*	Padusa by 1 dosa laval
Whatever the number of ANC	JZ I"	Reduce by 1 dose level

^{*} or until 28th day as needed (maximum)

Modalities of Reintroduction of treatment : ANC \geq 1500/mm³ and Platelets \geq 100 000/mm³ If the Platelets and/or ANC values are not correct at D28, the patient will discontinue permanently the study treatment.

At the time of Nadir

In the case of a grade 4 neutropenia, whatever the duration or complication i.e by an infection or fever > 38°5, the G-CSF will be administered at the next course of treatment. If the same toxicity continues with G-CSF then the irinotecan dose will be reduced at the dose immediately inferior. If there is a third occurrence of this toxicity, the patient will permanently discontinue the study treatment.

Table 5: Action and dose modification during the administration of Regorafenib in case of hematological toxicity

Hematological toxicity (Modification dose/delay for Regorafenib)			
Grade	Treatment delay	Dose modification	
Grade 0-2	No delay in Regorafenib	No modification dose	
Grade 0-2	treatment	No modification dose	
Grade 3	No delay in Regorafenib	Reduce by 1 dose levelbc	
Grade 3	treatment	heduce by Tuose level	
	Interrupt Regorafenib		
Grade 4	until hematologic	Reduce by 1 dose level ^{bc}	
	toxicity resolves to	heduce by Tuose level	
	Grade ≤ 2ª		

a If no recovery within 30 days, the treatment will be permanently discontinued.

- b If more than 2 dose reductions are necessary, the treatment will be permanently discontinued.
- c Cf table a.

Table 6: Action and dose modification during the administration of Regorafenib in case of non-hematologic toxicity

Non-hematological toxicity (dose modification/delay for Regorafenib) (except hand-foot skin reaction, hypertension, liver function test abnormalities and diarrhea)^a

Grade	Treatment delay	Dose modification
Grade 0-2	No delay in Regorafenib treatment	No dose modification
Grade 3	Interrupt Regorafenib until non hematologic toxicity resolves to Grade ≤ 2 ^b	Reduce by 1 dose level ^{cd}
Grade 4	Discontinue treatment permanently	Discontinue treatment permanently

- a In the absence of nausea/vomiting prophylaxis and diarrhea not treated.
- b If more than 2 dose reductions are necessary, the treatment will be permanently discontinued.

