	occurence	permanently	
> 20 times ULN (Grade 4)	Any	Discontinue regorafenib	
	occurence	permanently	
> 3 times ULN (Grade 2 or higher) with	Any	Discontinue regorafenib	
concomitant elevation of bilirubin > 2 times	occurence	permanently	
ULN		Control liver function every	
		week until resolution or	
		return to baseline	

Termination of Regorafenib:

- -In the event of gastrointestinal perforation or fistula develops
- -In the event of reversible Posterior Encephalopathy Syndrome (REPS)
- -In the event of the appearance of cardiac ischemia and/or infarction

Other toxicities

The other toxicities will have to manage symptomatically, if possible. For any toxicity grade \geq 2 at D15 except alopecia and anemia, the irinotecan will be delayed up to two weeks and the toxicity will have to be grade \leq 1 to perform the course.

ARM B: STIVARGA® (REGORAFENIB)

Dosage changes should be made in 40 mg increments (1 tablet). The recommended daily dose of Regorafenib is 160 mg.

Dose reductions of Stivarga ®
1st reduction: 120 mg
2 nd reduction: 80 mg

Table b

Table 10: Dose modification/Delay for toxicities related to study drug (except handfoot Skin reaction and hypertension)^a

NCI-CTC V5.0	Dose	Dose Modification	Dose for Subsequent Cycles
	Interruption		
Grade 0-2	Treat on time	No change	No change
Grade 3	Delay until <	Reduce 1 dose level ^c	If toxicity remains < Grade 2,

Protocole NEXT-REGIRI -Version 6.0 du 09/11/2023

Page 52 sur 86

	Grade 2 ^b		dose re-escalation can be
			considered at the discretion
			of the treating investigator.
			If dose is re-escalated and
			toxicity (Grade 3) recurs,
			institute permanent dose
			reduction.
Grade 4	Delay until <	Reduce by 1 dose level ^c .	
	Grade 2 ^b	Permanent discontinuation	
		can be considered at	
		treating investigator's	
		discretion.	

a Excludes alopecia, non-refractory nausea/vomiting, non-refractory hypersensitivity and asymptomatic laboratory abnormalities.

Table 11: Dose modifications for hand-foot skin reaction

Skin Toxicity Grade	Occurrence	Suggested Dose Modification
Grade 1: Numbness,	Any	Maintain dose level and institute immediately
dysesthesia, paraesthesia,		supportive measures for symptomatic relief
tingling, painless swelling,		
erythema or discomfort of		
the hands or feet which		
does not		
disrupt the patient's normal		
activities		
Grade 2: Painful erythema	1st	Decreasing dose by one dose level and institute
and	occurrence	immediately supportive measures.

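### An asymptomatic cytopenia is an adverse event by rule in the REGIRI arm but only by investigator judgement in the regorafenib arm, and liver tests are drawn twice as often in REGIRI, so the planned AE tables do not compare laboratory toxicity like for like.

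*Combined protocol and SAP*

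**What the plan says.** Section 10.1.1 restricts laboratory AEs: "Only abnormal laboratory findings which are clinically significant should be considered an AE". It ties significance to action: "Abnormal laboratory findings are clinically significant if an active medical intervention is indicated, such as a dose modification of the investigational product". The list of actions is open and also includes interruption, treatment, "the performance of additional diagnostic procedures; the increase in monitoring frequency".

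Section 6.3 gives the actions separately by arm.

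- **REGIRI (arm A).** Table 4 delays irinotecan when the day 15 neutrophil count is below 1500/mm3 with adequate platelets, and the dosing entry reads "No dose modification + G-CSF". Platelets below 100 000/mm3 lead to a delay and a dose reduction. If counts stay low: "If the Platelets and/or ANC values are not correct at D28, the patient will discontinue permanently the study treatment". Table 5 reduces regorafenib for grade 3 haematological toxicity, and interrupts and reduces it for grade 4. Table 6, for most other non-haematological toxicity, acts from grade 3. Neither Table 5 nor Table 6 exempts silent laboratory values.
- **Regorafenib (arm B).** Table 10 makes no change at grades 0-2. Its footnote a limits the table's scope: "Excludes alopecia, non-refractory nausea/vomiting, non-refractory hypersensitivity and asymptomatic laboratory abnormalities". There is no separate haematology table.

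For ALT and AST, Table 9 (arm A) and Table 13 (arm B) use the same bands and essentially the same actions.

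Section 9.3 plans descriptive safety tables by arm: "All AEs, as well as drug-related AEs and SAEs will be summarized by NCI-CTCAE version 5", with categories and worst grade. It also promises summaries of all safety parameters, but names no laboratory-grade table and no derivation from recorded values.

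**The concern.** Toxicity is a secondary objective and the natural counterweight to any survival gain. When a blood result becomes an AE only because an action is indicated, and the protocol prescribes that action in one arm only, part of the between-arm difference in laboratory AEs comes from the definition and not from the drugs. The direction is predictable: REGIRI would look relatively worse for silent cytopenias and other silent non-hepatic abnormalities. The irinotecan rules explain some of the asymmetry, but not all of it, because Table 5 and Table 10 both govern regorafenib.

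Sampling is a second, separate route. More scheduled draws give more chances to catch a transient abnormality, even where the classification rule is the same. The trial is open (section 3.1), so investigator discretion cannot be assumed to even out either effect.

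**Working it through.** The plan gives no figure to reproduce on this point. The check compares the rules, then counts scheduled draws.

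**1. Same result, both arms: is an action prescribed?**

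- Silent neutrophils < 1500/mm3 at day 15. Arm A: delay plus G-CSF (Table 4). Arm B: none from Table 10 if silent.
- Silent platelets < 100 000/mm3 at day 15. Arm A: delay plus reduction (Table 4). Arm B: none from Table 10 if silent.
- Silent grade 3 cytopenia. Arm A: regorafenib reduced (Table 5). Arm B: exempt under footnote a.
- Silent grade 3 non-haematological, non-hepatic laboratory value. Arm A: interrupt and reduce (Table 6). Arm B: exempt under footnote a.
- ALT/AST up to 5 x ULN. Both arms: continue with weekly liver tests, which is itself increased monitoring and so meets the AE test.
- ALT/AST > 5 to 20 x ULN, or > 20 x ULN. Both arms: same interruption or discontinuation rule.
- Dipstick protein 3+ or more. Both arms: 24-hour collection (section 5.3), an additional diagnostic.

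The classification differs for blood counts and silent non-hepatic results that have no rule of their own. It does not differ for ALT/AST or for dipstick proteinuria.

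**2. Size of the classification effect.** The documents give neither the rate of silent cytopenia nor the rate of discretionary reporting. Let T be the true proportion of patients affected, equal in both arms and sampled equally, and let r (0 to 1) be the share that arm B investigators report. The AE table then shows T in arm A and rT in arm B, a spurious difference of (1 - r)T. This is zero if r = 1 and T if r = 0. No narrower figure can be justified.

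**3. Scheduled liver draws, cycles 1-2** (schedule in 5.1 with its footnote 2; day 8, 15 and 22 lists in 5.3).

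- Arm A: D1, D8, D15, D22, so 4 x 2 = 8.
- Arm B: D1, D15, so 2 x 2 = 4.

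Assume an independent chance p of an abnormal value per draw, the same in both arms. The chance of at least one is 1 - (1 - p)^k.

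- p = 0.05: 1 - 0.95^8 = 33.7% versus 1 - 0.95^4 = 18.5%.
- p = 0.10: 1 - 0.90^8 = 57.0% versus 1 - 0.90^4 = 34.4%.
- p = 0.20: 1 - 0.80^8 = 83.2% versus 1 - 0.80^4 = 59.0%.

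These counts include C1D1, which eligibility largely screens and which may be skipped if tests were done within 7 days. Without it the draws are 7 versus 3. At p = 0.10 that gives 1 - 0.90^7 = 52.2% versus 1 - 0.90^3 = 27.1%, so the gap remains.

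**4. Scheduled blood counts, cycles 1-2.** Arm A has D1 and D15, so 4. For arm B, the schedule table in 5.1 and the short arm B day 15 list in 5.3 imply D1 only, so 2. The general treatment-period text in 5.3 asks for D1 and D15 tests in both arms, so 4. Under the general text there is no sampling difference; under the table there is. The documents do not settle which applies.

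**The case against.** The strongest reply is that the AE test asks whether an intervention is indicated, not whether a dose table prescribes one. The list is open, and footnote a limits a dosing table; it is not a reporting rule. An arm B investigator who repeats a count or treats a cytopenia makes it an AE. The grade descriptions in section 10.1.3 add to this. Grade 4 is described in terms of urgent intervention, so a grade 4 value probably qualifies in either arm, and grade 3 has a good case. All of this stands.

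A reader might therefore infer too much: that identical blood results are AEs in REGIRI and never in regorafenib, that arm B would record none, or that silent grade 3-4 values are hidden there. The documents do not support these readings. Nor do they support a hepatic classification bias, because Tables 9 and 13 match in substance.

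It can also be said that section 2.2.2 has safety assessed by clinical and biological means and scored by CTCAE, that section 9.3 covers all safety parameters, and that a SAP is still to come. These point towards laboratory grading, but they do not state it and do not neutralise the AE rule. Finally, weekly testing after an elevation narrows the liver-test gap in worst grade. It does not restore the first detections that arm B's fewer scheduled draws may miss.

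**Conclusion.** The point holds in a limited form. For blood counts and other silent non-hepatic results without a rule of their own, AE status follows from protocol rule in REGIRI and from investigator judgement in regorafenib. That biases the descriptive AE comparison against REGIRI by an amount the documents do not allow one to estimate.

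For liver tests only the sampling differs: 8 versus 4 scheduled draws in cycles 1-2. That would give 34-83% versus 19-59% of patients with at least one abnormal value, assuming equal true risk, independence between draws and 5-20% per draw. Correlation within patients would change these figures. Blood-count sampling is contradictory and may be equal.

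The overall survival test is unaffected, and no formal safety test is planned. This is worth correcting because toxicity is a stated objective and the remedy is cheap.

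**What to change.** In section 9.3, or in the SAP that it announces:

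- Add a table of worst CTCAE v5.0 grade derived from recorded laboratory values in both arms, whatever action was taken. State that it is the basis for comparing laboratory toxicity.
- Add a supplementary version limited to draws scheduled in both arms.
- Keep the investigator-reported AE tables as planned, and leave the section 10.1.1 definition in place for vigilance.

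In section 5, reconcile the day 15 sampling: the general text of 5.3 against the schedule table in 5.1, its footnote 2 and the arm-specific day 15 lists. The dose rules need not change for this purpose.

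The cost is one or two extra programmed tables and no new tests. This assumes that laboratory values and site normal ranges are in the eCRF, which section 11.1 does not say. Common-draw rates will understate total toxicity, so that version should stay supplementary.
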